SURVEILLANCE AND ALERT-BASED MULTIPARAMETER MONITORING TO REDUCE WORSENING HEART FAILURE EVENTS - SCALE-HF 1

A prospective, multicenter study designed to evaluate how the Bodyport Cardiac Scale and biomarkers change with worsening heart failure

> Principal Investigator: [name], MHS Duke Clinical Research Institute Draft or Version Number: 2.0 2 March 2021

LIST OF TABLES AND FIGURES

Table 1.	List of Abbreviations	2
Figure 1.	SCALE-HF Overall Design	5
Table 2.	SCALE-HF 1 Schedule of Events	8

ABBREVIATIONS

Table 1. List of Abbreviations

Ballistocardiograph		
Code of Federal Regulations		
Duke Clinical Research Institute		
Electrocardiograph		
Good Clinical Practice		
Heart Failure		
Heart failure with reduced ejection fraction		
Heart failure with preserved ejection fraction		
Impedance plethysmograph		
Left Ventricular Ejection Fraction		
United States		

STATEMENT OF COMPLIANCE

The trial will be carried out in accordance with Good Clinical Practice (GCP) as required by the following:

- United States Code of Federal Regulations (CFR) applicable to clinical studies (45 CFR Part 46, 21 CFR Part 50, 21 CFR Part 56, 21 CFR Part 312, and/or 21 CFR Part 812)
- International Council on Harmonisation (ICH) E6

I agree to ensure that all staff members involved in the conduct of this trial are informed about their obligations in meeting the above commitments.

Principal Investigator: [name], MHS

Signed: _____

Date:				

PROTOCOL SUMMARY

Title:	SurveillanCe and Alert-based multiparameter monitoring to reducE
ince.	worsening Heart Failure events – SCALE-HF 1
Summary:	The overarching goal of this prospective, multicenter study is to utilize data from the Bodyport Cardiac Scale to develop an algorithm that allows for the early detection of worsening heart failure (HF). The Bodyport Cardiac Scale is capable of measuring key HF parameters of congestion and cardiac perfusion on a regular basis in a patient's home. These data will be combined into a model or composite index that may be used to identify patients at increased risk for decompensation, inform the reason for their decline, and offer the possibility to remotely optimize therapy to prevent further worsening HF.
	The SCALE-HF program will consist of multiple phases. For SCALE-HF 1, patients will be prospectively enrolled and utilize the Bodyport Cardiac Scale on a daily basis. Patients and clinicians will be blinded to the results other than data readily available from other devices such as body weight. There will be no attempt to influence clinical practice. Patients will be followed remotely for suspected clinical events.
Objectives:	The primary objective of this study is to utilize data from the Bodyport Cardiac Scale to develop a model that allows for the early detection of worsening HF.
Endpoints:	The primary endpoint of the study will be worsening HF. Worsening HF will be defined as an urgent, unscheduled clinic or emergency department visit or hospital admission with a primary diagnosis of HF in which the patient exhibited new or worsening symptoms of HF on presentation, had objective evidence of new or worsening HF, and received initiation or intensification of treatment for HF.
Design	 This study is intended to enroll a broad population of patients. Patients may be consented and enrolled remotely, in clinic, or prior to hospital discharge. Training on device use will be provided and daily utilization will be requested. Device sensor data will be uploaded remotely and analyzed on a continuous basis. Treating clinicians will be blinded to the investigational sensor data. Follow-up will occur remotely at 6 weeks, 3 months and then every 3 months until the end of the study. Patients may also be contacted by the
	site and/or study team for suspected device malfunction or nonadherence with the Bodyport Cardiac Scale. At each interview, participants will be asked to report possible clinical events. Sites may also be queried to report possible clinical events. All patients will consent to release of medical records regarding HF history
	and suspected clinical events. Based on site- and participant-reported events, medical billing data and medical records for possible clinical events will be collected. Possible clinical events will be reviewed and adjudicated

	by a clinical events committee using standardized definitions. The committee members will be blinded to sensor and algorithm data.
Population:	 Approximately 300 male and female participants in the US, 18 years of age or older, irrespective of left ventricular ejection fraction with symptomatic HF will be enrolled. Patients must be able to stand independently on the Bodyport Cardiac Scale. We will exclude patients with a weight > 170 kg, prior heart transplant or currently listed for heart transplant, current LVAD, current inotropes, and end-stage renal disease requiring chronic dialysis.
Sites Enrolling	Approximately 5 US sites
Participants:	
Duration of Study	Approximately 1 year (6 months enrollment and approximately 6 months follow up)
Study Product	Bodyport Cardiac Scale

Figure 1. SCALE-HF Overall Design. Scale-HF 1 will be the first in a series of studies that aims to evaluate the use of the Bodyport Cardiac Scale to rapidly identify early worsening HF in order to allow for clinical interventions to prevent disease progression.

2. BACKGROUND AND TRIAL RATIONALE

2.1 BACKGROUND INFORMATION

Heart failure (HF) is a major health, social and economic problem worldwide.¹ The incidence and prevalence of HF are increasing,² in part due to an aging population and rising burden of comorbidities.³ Efforts to decrease mortality, decrease hospitalization rates and improve the well-being of patients with HF were modestly successful over the last decade with the introduction of medical therapies and care strategies.⁴ However, despite advances in medical and device therapies, the number of hospitalizations for HF and associated readmissions remains high and represents an increasingly unsustainable financial burden.⁵ As a result, reducing HF readmission rates has become a priority in many of the developed countries. In the US alone, the costs related to HF are expected to reach \$70 billion by 2030, an increase of 130% on current costs.⁶⁻⁸

Achieving and maintaining an euvolemic status is a key goal in the management of HF. Thus, close observation of, and rapid response to changes in early physiological indicators are essential in achieving or maintaining euvolemia. Clinical signs and symptoms of HF decompensation are preceded by an increase in filling pressures, autonomic adaptation and resultant cardiac function and total fluid content changes.

The Bodyport Cardiac Scale provides an innovative and noninvasive approach to obtain clinically relevant hemodynamic parameters. The Bodyport Cardiac Scale is a physical platform in which the user stands with bare feet. The scale captures a number of physiological parameters including weight, electrocardiogram, impedance plethysmography and ballistocardiography to derive a proprietary

algorithm to monitor for cardiac decompensation through a preceding change in heart rate, cardiac output, stroke volume, cardiac time intervals, body weight and other biomarkers. Bodyport Cardiac Scale biomarkers are transmitted to a HIPAA-compliant cloud via an integrated cellular LTE-M modem for storage and visualization in a web-based application. The simplicity of the Bodyport Cardiac Scale enables patients to use the system at home, allowing patients to be monitored remotely and make treatment decisions with their medical team without the need for an in-person visit.

2.2 RATIONALE

Despite recent advancements in medical therapy, many patients with HF continue to have a high burden of symptoms and are at increased risk for adverse outcomes. As noted above, management of worsening HF also represents a major economic burden on the public health system. Worsening HF is characterized by the need for rehospitalization or urgent outpatient treatment for acute HF in order to control symptoms, preserve end organ function, and prevent further disease progression including death. There remains an urgent need to detect early worsening HF in order to allow for clinical interventions to prevent disease progression.

2.3 POTENTIAL RISKS

The known risks to participants in the trial will be minimal, as SCALE-HF 1 will be limited to data collection. Risk is involved to the extent that privacy and confidentiality may be compromised. However, every reasonable effort will be made to limit breaches of privacy and confidentiality.

3. OBJECTIVES AND ENDPOINTS

3.1 PRIMARY OBJECTIVES

The primary objective of this study is to utilize data from the Bodyport Cardiac Scale to develop an algorithm that allows for the early detection of worsening HF.

3.1 SECONDARY OBJECTIVES

The secondary objectives of this study are to compare data from the Bodyport Cardiac Scale to:

- Data obtained from approved implantable devices and sensors
- Data obtained from other markers of congestion including invasive hemodynamics, biomarkers, and blood volume analysis

3.2 ENDPOINTS

The primary endpoint of the study will be worsening HF.

Worsening HF will be defined as an urgent, unscheduled clinic (requiring IV diuretics) or emergency department visit or hospital admission with a primary diagnosis of HF in which the patient exhibited new or worsening symptoms of HF on presentation, had objective evidence of new or worsening HF, and received initiation or intensification of treatment for HF.

Information will also be collected on death and any mortality events will be classified as cardiovascular or non-cardiovascular. We will also collect data on arrhythmic events requiring hospitalizations or a defibrillator shock where the collected data allows such an assessment.

4.1 OVERALL STUDY DESIGN

SCALE-HF 1 is a prospective, multicenter study. The overarching goal is to enroll a broad population of patients with HF and follow them remotely for clinical events. Patients will be identified by participating sites and may be consented and enrolled remotely, in clinic, or prior to hospital discharge. Follow-up visits will be remote and occur at 6 weeks, 3 months and then every 3 months until the end of the study. Follow-up information will be collected by sites and may be supplemented by a centralized telephone call center (and email) via trained personnel at the Duke Clinical Research Institute. Participants may also be contacted by the site and/or study team at other timepoints for study issues such as suspected device malfunction or nonadherence with the Bodyport Cardiac Scale.

Patients eligible for the study will have HF and a prior history of hospitalization for acute decompensated HF. A history of clinical HF will be confirmed by site investigators. To ensure that a broad population of patients is enrolled, there will be limited additional inclusion and exclusion criteria. The participant population is described in more detail in Section 5 below.

All patients will consent for longitudinal follow-up. This will include remote follow-up visits as well as access to clinical records to evaluate for future clinical events. The remote follow-up visits will place a minimal burden on patients and sites and be limited to assessments for suspected clinical events. All patients will consent to release of medical records regarding HF history and suspected clinical events. Based on site- and participant-reported events, medical records for possible clinical events will be collected. Possible clinical events will be reviewed and adjudicated by a clinical events committee using standardized definitions. The committee members will be blinded to sensor and algorithm data.

Training on device use will be provided to patients and daily utilization of the Bodyport Cardiac Scale will be requested. Device sensor data will be uploaded remotely and analyzed on an ongoing basis throughout the study. Patients, study teams, and treating clinicians will be blinded to the investigational sensor data other than basic information that is currently available through other devices including weight, heart rate and leg edema status. There will be no attempt to utilize the study data to influence clinical practice.

4.2 SCHEDULE OF EVENTS

	Baseline Visit	Follow-up Visits
Eligibility criteria	Х	
Informed consent	Х	
Demographics ^a	X	
Laboratory evaluations ^b	Х	
Electrocardiogram	X	

Table 2. SCALE-HF 1 Schedule of Events

Relevant medical history ^c	Х	
Implantable device data ^d		Х
HF outcomes ^e		Х
Arrhythmic events requiring hospitalizations ^f		Х

^a Includes date of birth, sex, race, ethnicity

^b Includes most recent basic metabolic panel (sodium, potassium, blood urea nitrogen, serum creatinine) and natriuretic peptide levels, B-type natriuretic peptide (BNP) or N-terminal pro-BNP. Where available will collect right heart cath data. ^c Includes heart failure history including last assessment of left ventricular ejection fraction

^d Patients with cardiac implantable electronic devices including pulmonary artery sensors and implantable cardioverter defibrillators will provide routine interrogation data

^e Hospital readmissions and all-cause mortality.

^fHospitalization event or treatment for ventricular arrhythmia (shock by defibrillator)

5. STUDY POPULATION

5.1 INCLUSION CRITERIA

Participants eligible for inclusion in this study must fulfill all of the following criteria:

- 1. Provide informed consent before trial enrollment
- 2. Age ≥ 18 years
- 3. A diagnosis of symptomatic HF including a worsening HF event in the preceding 12 months. Worsening HF events will be determined by local clinician-investigators and will typically include the following: a) HF symptoms (eg, dyspnea, fatigue); b) HF signs (eg, elevated jugular venous pressure, peripheral edema), or laboratory/imaging evidence of HF (eg, pulmonary congestion on chest x-ray, elevated natriuretic peptide levels) during the event, and treatments targeting acute HF (eg, intravenous diuretics, vasodilators, or inotropes).

5.2 EXCLUSION CRITERIA

Patients fulfilling any of the following criteria are not eligible for inclusion in this study. No additional exclusions may be applied by the investigator, in order to ensure that the trial population will be representative of all eligible participants.

- 1. Weight > 170 kg
- 2. Use of chronic inotropic therapy
- 3. Prior heart transplant or currently listed for heart transplant
- 4. Current or planned left ventricular assistance device
- 5. Chronic kidney disease requiring chronic dialysis
- 6. Unknown left ventricular ejection fraction (LVEF). The LVEF should be based on the most recent local measurement using echocardiography, multigated acquisition scan, computed tomography scanning, magnetic resonance imaging, or ventricular angiography. Patients with preserved and reduced LVEF will be permitted in the study though enrollment may be capped to ensure no

more than approximately 2/3 of the total enrollment includes patients with preserved or reduced LVEF.

- 7. Terminal illness other than HF, such as malignancy, or with a life expectancy of less than 1 year as determined by the enrolling clinician-investigator
- 8. Unable to participate in longitudinal follow-up including daily use of the Bodyport Cardiac Scale. Patients must be able and willing to stand independently on the Bodyport Cardiac Scale daily.

6. STUDY VISITS AND ACTIVITIES

6.1 SCREENING AND ENROLLMENT

Patients will be identified from outpatient clinic logs as well as current admission panels. Patients previously included in clinical trials will also be screened for candidacy. Eligible candidates will be enrolled from an outpatient setting or an inpatient setting. Enrollment will be capped to ensure that no more than approximately 2/3 of the total enrollment will be at the time of hospital discharge or from the outpatient setting.

Prior to screening activities, each patient will be given an opportunity to ask questions and to understand the details of study participation, including risks and benefits. This consent process will be documented in the patients' source documents and evidenced by the patient signing the informed consent form (ICF). All patients will consent to release of medical records regarding HF history and suspected clinical events. Informed consent will be obtained either in person or via e-consent according to respective institutional policies.

After signing the ICF, each patient will be assigned a unique identifier number that will be used on all documentation.

Screening data will be collected after informed consent is signed. The Screening evaluations include:

- Informed Consent
- Inclusion/Exclusion Criteria
- Demographics
- Medical history
- Most recent physical examination, biomarkers (NT-proBNP, basic metabolic panel) and vital signs measurements
- Current medications
- Recent laboratory data including renal function and natriuretic peptide values

If measurement of any of the above assessments does not occur in the normal course of patient care, clinical practice should not be changed to accommodate collection of additional data.

Following enrollment, the patient will be provided with the study device and receive training in person or remotely on its use from study coordinators or company representatives.

1. Outpatient- Enrollment can occur in person or remotely. Scale will be provided upon clinic visit or shipped to patient directly after the appointment

2. Inpatient- Patient is enrolled prior to discharge. Scale will be provided prior to discharge or shipped by Bodyport Inc. to patient directly after the discharged

6.2 SURVEILLANCE/FOLLOW UP

Follow-up will occur remotely at 6 weeks, 3 months and then every 3 months until the end of the study. Follow-up will occur via telephone interviews by trained personnel by individual participating sites. This approach will ensure the consistency and quality of data collection and minimize loss to follow-up. At each interview, participants will be asked to report any encountered clinical events.

Routine data collection at each follow up timepoint will include:

• Possible clinical event including those that occur outside of the enrolling health system such as hospitalization, emergency room visit or clinic visit with IV diuretic administration

Based on participant-reported events, clinical data for rehospitalizations, emergency department visits, and worsening heart failure related clinic visits will be obtained and submitted for review. As an additional mechanism to safeguard against under-reporting of events, sites will conduct medical record queries at 6 weeks, 3 months and then every 3 months until the end of the study enrollment to screen for hospitalizations or procedures.

Patients may also be contacted by the site and/or study team including the sponsor and coordinating center for suspected device malfunction or nonadherence with the Bodyport Cardiac Scale. Nonadherence is defined as device non-use for 3 days or more. Patients will be potentially contacted using email, phone calls or text messaging to provide reminders to use the scale. Should non-use continue beyond 4 days the patient may be contacted by a phone call to explore potential problems with the technology or explore whether an event might have occurred.

Upon study discontinuation the patients are asked to return the scale to the company and are provided with a return shipping label.

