10.3 SAMPLE SIZE

Data derived from this study will add to the model development aims of the Bodyport Cardiac Scale. This study is statistically powered to detect approximately 75 primary endpoints which will approximate to about 300 enrolled patients. An event rate of 75 equates to an approximate rate of 25% at 6 months. Given that this study is a development study however additional events may be required to derive the predictive algorithm.

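### Section 6.2 ends the site record queries at the close of study enrollment while the interviews run to the end of the study; followed literally, most expected events would come after a patient's last scheduled record check.

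*Protocol*

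**What the plan says.** Section 6.2 describes two ascertainment activities with the same time points and different stop points.

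- Interviews: "Follow-up will occur remotely at 6 weeks, 3 months and then every 3 months until the end of the study".
- Record queries: "sites will conduct medical record queries at 6 weeks, 3 months and then every 3 months until the end of the study enrollment". Their purpose is given as "As an additional mechanism to safeguard against under-reporting of events".

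The same section makes the patient's report the first trigger for collecting endpoint records: "Based on participant-reported events, clinical data for rehospitalizations, emergency department visits, and worsening heart failure related clinic visits will be obtained".

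The Protocol Summary (Duration of Study) treats enrollment and follow-up as separate periods: "Approximately 1 year (6 months enrollment and approximately 6 months follow up").

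Section 10.3 gives the expected yield: "This study is statistically powered to detect approximately 75 primary endpoints which will approximate to about 300 enrolled patients", and "An event rate of 75 equates to an approximate rate of 25% at 6 months".

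**The concern.** Taken at its word, section 6.2 withdraws the safeguard when the last patient is recruited, about halfway through the study. Late enrollees would have little or no record checking, so the quality of outcome ascertainment would depend on enrollment date. If sites read the phrase differently, it would also depend on site.

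This matters because the study exists to develop an alert algorithm (section 3.1), and candidate models are to be judged on sensitivity and specificity for heart failure events (section 10.1). If an event is never reported, the scale data before it are labelled event-free. A correct alert in that window is then scored as false, and the event is lost to model development. Section 10.3 already allows that more events than planned may be needed. Adjudication does not repair this, because the committee can review only the events that reach it.

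**Working it through.** **Inputs from the Protocol.** Queries at 1.5, 3 and then every 3 months after entry (6.2); enrollment of 6 months followed by about 6 months of follow-up (Summary); 300 patients, 75 events, 25% at 6 months (10.3).

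**Assumptions, not in the Protocol.** Entry is uniform over 6 months, the hazard is constant, and each patient is followed for 6 months. Each is varied below.

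**The plan's own figure.** 300 × 0.25 = 75 events, which reproduces.

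**Last query on the literal reading.** A patient entering at month t has been on study for 6 − t months when accrual closes.

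| Entry month t | Share of patients | Last query |
|---|---|---|
| 0 to 3 | 50% | 3 months |
| 3 to 4.5 | 25% | 1.5 months |
| after 4.5 | 25% | none |

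Only a patient entering at the very start reaches the 6-month query. The mean time of the last query is 0.50 × 3 + 0.25 × 1.5 + 0.25 × 0 = 1.875 months.

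**Share of events after the last query, 6 months of follow-up each.**

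- Constant rate, all events: 1 − 1.875/6 = 68.75%, or 0.6875 × 75 ≈ 52 events.
- First events, exponential: h = −ln(0.75)/6 = 0.0479 per month. The probability of an event by 3 months is 1 − exp(−3h) = 0.1340, and by 1.5 months 1 − exp(−1.5h) = 0.0694. Expected events before the last query are 300 × (0.50 × 0.1340 + 0.25 × 0.0694) = 25.3. That leaves 49.7 of 75 after it, or 66.3%.

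**Sensitivity.** With a common close-out at month 12, mean follow-up is 9 months and the constant-rate share is 1 − 1.875/9 = 79.2%. The front-loaded hazard uses S(t) = exp(−c·t^k) with c = −ln(0.75)/6^k. Early and late accrual are triangular over the 6 months.

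| Scenario | 6 months each | Common close at month 12 |
|---|---|---|
| Uniform accrual, constant rate | 68.75% | 79.2% |
| Uniform accrual, first events, exponential | 66.3% | 75.8% |
| Uniform accrual, front-loaded, k = 0.7 | 57% | 66% |
| Uniform accrual, front-loaded, k = 0.5 | 50% | 58% |
| Early accrual, constant rate | 58% | 75% |
| Late accrual, constant rate | 80% | 85% |

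The range is about 50% to 85%. It varies hazard and accrual separately. The most favourable pairing, early accrual with k = 0.5 and 6 months each, goes lower. The shares with a last query at 3 and 1.5 months become 75% and 18.75%, the event probabilities by those times are 0.184 and 0.134, and the result is 1 − (0.75 × 0.184 + 0.1875 × 0.134)/0.25 ≈ 35%.

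**After the fix.** With 6 months per patient, the 6-month query closes the window and nothing falls after it. With a common close-out at month 12, half the patients have their last query at 6 months and half at 9, so the mean is 7.5 and 1 − 7.5/9 = 17% of follow-up time remains after it, against 79% on the current wording.

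**The case against.** The strongest reply is that the phrase is a slip. The queries run on the same patient-level clock as the interviews, and on the literal reading the three-monthly continuation would apply to almost nobody. A reading that empties the sentence's own schedule is unlikely to be what was planned. If the phrase meant a patient's time in the study, there is no gap. This is a fair account of the probable intent, but it does not settle what sites will do. Elsewhere the Protocol uses enrollment for recruitment or entry (Summary; sections 5.1, 5.2, 6.1 and 10.2), and the interview sentence in the same section shows how the end of the study is expressed when that is meant.

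A reader might also infer that after accrual closes, ascertainment rests on patients' telephone recall alone. The Protocol does not support that. The Summary says sites may also be asked to report possible events, and section 4.1 refers to site-reported events and to access to clinical records. Section 6.2 allows a call after continued device non-use, partly to find out whether an event has happened, and a hospital stay could well produce such a gap. None of these routes is tied to accrual. They are, however, optional, triggered or without a set schedule, so they do not replace a scheduled record check of every patient.

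Finally, constant hazard is open to doubt. Every patient has had a worsening event in the preceding 12 months (5.1) and many may enroll at discharge (6.1), so events may cluster early. This objection stands, and it is why the result is given as a range.

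**Conclusion.** The two stop points in section 6.2 do not match and should be reconciled. This is an inconsistency of wording with a possible operational consequence; the documents do not show a deliberate choice to stop the queries early.

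If the text is followed literally and accrual is uniform, 25% of patients get no record query, 25% get one at 6 weeks only, and about two thirds of expected events come after a patient's last query. That last figure rests on constant hazard and 6 months of follow-up each; the range is roughly 50% to 85% in the scenarios that vary hazard or accrual separately, and lower if early accrual and early clustering of events coincide.

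A reader might take the two thirds as a share of events lost. It is not. It counts events without one backup check, while the interviews and other routes continue. The Protocol gives no under-reporting rate, so the number of events actually missed or mislabelled cannot be estimated. What can be said is that the only scheduled record check would be absent for much of follow-up, unevenly by enrollment date, and that any unreported event would bias sensitivity and specificity.

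**What to change.** In section 6.2, replace the stop point in the record-query sentence with the one used for the interviews, the end of the study, and state that for each patient this means the end of that patient's follow-up. Queries and interviews then share both time points and stop point.

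A final record query at close-out is optional. It matters only if follow-up runs past the last scheduled query, as it would for many patients under a common close-out.

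The cost is a one-phrase amendment and one or two further rounds of a query that sites already perform.

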10. STATISTICAL METHODS AND DATA ANALYSIS

10.1 STATISTICAL AND ANALYTICAL PLANS

The Bodyport Cardiac Scale captures various physiological signals including an electrocardiograph, an impedance plethysmograph, and a ballistocardiograph. These raw signals will be filtered and interpolated prior to feature extraction and model validation. Regions with motion artifacts or noise will be identified and removed. Ensemble average waveforms will be constructed from the real-time signals. Specific characteristic features will be identified on the averaged waveforms. Temporal and amplitude-based biomarkers will be extracted from the identified features within and across each averaged waveform. These features and biomarkers will be assessed longitudinally by constructing trends consisting of multiple measurements and identifying statistically significant changes over time. Some of the key features being explored in this study are: weight, heart rate, heart rate variability, peripheral impedance, body fluid, balance, stroke volume, cardiac output, pre-ejection period, left ventricular ejection time, as well as the amplitude and timing of characteristic features on the IPG, ECG, and BCG signals. A focus on these specific features is driven by prior research demonstrating clinical relevance to cardiovascular function and heart failure status.

During analysis, various methods will be implemented to select signal features that demonstrate a meaningful association with HFEs. Those features most strongly correlated to HFEs will be combined into a model and associated alert algorithm. The development of the model may use a combination of techniques, including multivariate regression and machine learning (e.g. support vector machines, clustering, decision trees, Bayesian networks). Models will be evaluated and optimized based on their sensitivity and specificity to detect heart failure events.

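### The only mandatory record check for unreported events omits two of the three primary-endpoint routes, and its stop point is worded differently from that of the interviews

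*Protocol*

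**What the plan says.** Section 3.2 defines the primary endpoint as an "urgent, unscheduled clinic (requiring IV diuretics) or emergency department visit or hospital admission with a primary diagnosis of HF", with further conditions on symptoms, objective evidence and treatment.

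Section 6.2 sets up two scheduled ways of finding events:

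- **Interviews.** These take place at 6 weeks, 3 months and every 3 months thereafter to the end of the study. They ask about "hospitalization, emergency room visit or clinic visit with IV diuretic administration", including events outside the enrolling health system.
- **Site record queries.** These follow the same timetable, are worded as an obligation, and are described as the extra protection against under-reporting. They run "until the end of the study enrollment to screen for hospitalizations or procedures".

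Table 2, footnote e (section 4.2), describes the HF outcomes collected at follow-up as "Hospital readmissions and all-cause mortality".

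Other routes are mentioned elsewhere. The Protocol summary (Design) says: "Sites may also be queried to report possible clinical events". Section 4.1 says: "Based on site- and participant-reported events, medical records for possible clinical events will be collected". On timing, the Protocol summary gives the study duration as "Approximately 1 year (6 months enrollment and approximately 6 months follow up").

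**The concern.** The safeguard is narrower than the endpoint it protects. It covers admissions and also procedures, which are not part of the endpoint. It does not name emergency-department visits or IV-diuretic clinic visits, which are.

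The adjudicated events are the labels on which the algorithm is built. Section 10.1 states: "Models will be evaluated and optimized based on their sensitivity and specificity to detect heart failure events". An emergency or clinic event that nobody reports leaves the development set, and a correct alert before it is counted as a false positive. Admissions have a second chance of being found and the other two routes do not, so under-detection is uneven by event type and tilts the labels towards admissions.

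A second, separate point is the stop date. Interviews continue to the end of the study, whereas queries continue to the end of study enrollment. The Protocol summary uses enrollment for the 6-month accrual period and distinguishes it from follow-up.

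**Working it through.** **1. The plan's own figure.** Section 10.3 gives about 300 patients and 25% with an event at 6 months: 300 × 0.25 = 75 endpoints. This reproduces.

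**2. Scope, route by route.**

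| Endpoint route (3.2) | Interview (6.2) | Mandatory record query (6.2) | Table 2, footnote e |
|---|---|---|---|
| Hospital admission | yes | yes | yes |
| Emergency-department visit without admission | yes | not named | not named |
| Urgent clinic visit with IV diuretics | yes | not named | not named |

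The remaining routes do not fill the empty cells:

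- Site queries (Protocol summary) and the central call center (4.1) are optional.
- Collection of medical records (Protocol summary, 4.1) and of billing data (Protocol summary) follows a report by the patient or site, so it cannot reveal an unreported event.
- The phone call after more than 4 days of device non-use (6.2) is optional.

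**3. Cost of one missed event.** Take one event per patient.

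- Endpoints lost: 1/75 = 1.3%.
- Apparent non-event patients: 300 − 75 + 1 = 226. If the missed patient had alerted, patient-level specificity falls by 1/226 = 0.44 percentage points.

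**4. Scope scenarios (assumed inputs, not in the protocol).** Suppose 10% to 40% of endpoints are emergency or clinic visits without admission. Then 75 × 0.10 = 7.5 to 75 × 0.40 = 30 endpoints have no mandatory record check. Suppose also that 10% to 30% of those go unreported:

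- Low: 7.5 × 0.10 = 0.75 events lost; observed rate (75 − 0.75)/300 = 24.75%.
- High: 30 × 0.30 = 9 events lost; observed rate (75 − 9)/300 = 22.0%.

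**5. Stop point, only if study enrollment means accrual.** Let u be the entry time on 0 to 6 months, with queries ending at calendar month 6. The share of person-time after month 6 is mean(u)/6 if everyone is followed for 6 months, or 6/(12 − mean(u)) if everyone is followed to month 12.

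| Accrual (assumed) | Mean u | 6 months each | Common end at month 12 |
|---|---|---|---|
| Uniform | 3 | 3/6 = 50% | 6/9 = 67% |
| Front-loaded triangular | 2 | 2/6 = 33% | 6/10 = 60% |
| Back-loaded triangular | 4 | 4/6 = 67% | 6/8 = 75% |

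Queries reached under uniform accrual, taking 6 weeks as 1.5 months:

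- The 6-week query needs u ≤ 4.5, which is 75% of patients. The other 25%, or 75 of 300, get no scheduled query. Taking 6 weeks as 42 days raises the 75% to 77%.
- The 3-month query needs u ≤ 3, which is 50%, or 150 patients.
- The 6-month query needs u = 0, so effectively nobody reaches it.

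The share with no query is (1 − 0.75)² = 6% under front-loaded accrual and 1 − 0.75² = 44% under back-loaded accrual.

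If study enrollment means each patient's time in the study, the time gap is 0%.

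**The case against.** **The stop point is probably a slip.** The query timetable matches the patient-based interview timetable. If queries ended with accrual, the instruction to continue every 3 months would have no content, because no patient would reach the 6-month query. This is a good argument and makes participation the likelier meaning. The accrual figures are therefore conditional and secondary. The wording still needs correcting, because a site could follow it literally.

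**The scope gap is narrower than it first looks.** An emergency visit that ends in admission is a hospitalization and falls within the query. Only emergency visits without admission and IV-diuretic clinic visits are exposed, and only when neither patient nor site reports them. This stands and limits the size of the problem. It does not remove it, since both routes count towards the endpoint on their own.

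**Other ways of finding events exist.** Interviews cover all three routes at every time point, and the call after device non-use may prompt a report. The query is only a back-up. That is so, but the call is optional, and a back-up against under-reporting is of use precisely where the interview fails.

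**The effect is not sized.** The figures of 1.3% and 0.44 points are costs per event, and section 10.1 does not say that specificity is measured per patient. Section 10.3 also calls this a development study that may need more events. All of this stands, and no estimate of the total loss is claimed. Footnote e is a short table note and is weak evidence on its own; aligning it is editorial.

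**Conclusion.** The concern holds and should be fixed. On the text of section 6.2, the only scheduled and mandatory record screen leaves out two of the three endpoint routes in section 3.2, and nothing else in the protocol gives them an equivalent check. This conclusion needs no assumption.

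The number of endpoints lost cannot be derived from the protocol. Each costs 1.3% of the planned 75 and, where an alert preceded it, about 0.4 points of patient-level specificity, assuming one event per patient. The range of 0.75 to 9 lost events is illustrative and rests wholly on the assumed event mix and reporting failure.

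The stop-point discrepancy is a wording conflict to resolve. Its effect is 0% of person-time if participation is meant. If accrual is meant, it is 50% to 67% under uniform accrual and 33% to 75% across the accrual patterns tried.

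**What to change.** In section 6.2, have sites query medical records at each follow-up time point through each participant's last follow-up, and name all three targets: hospitalizations, emergency-department visits, and clinic visits with IV diuretics. Align Table 2 footnote e with the section 3.2 endpoint plus death.

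The cost is two wording changes and slightly broader searches in records the sites already query. No visit or procedure is added, and the planned 300 patients and 75 endpoints do not change. Site queries may still miss care given outside the enrolling system, for which the interviews remain necessary. The gain is that all three endpoint routes get the same check for the same length of time.
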